8.3 Planned interim analyses

No formal interim analysis of the main study treatment phase is planned given that it is a small pilot study.

8.4 Determination of sample size

This is a pilot study. With a total sample of 30 participants (15 per treatment group), and to produce a 95% confidence interval of the difference in means between the two treatment groups, the width of the confidence interval would be +/- 0.374.

9. Data handling and quality assurance

9.1 Data recording

All data will be entered into the RDMS system. A source document checklist will be used at the site to identify the source data for all data points collected. .

9.2 Archiving

Documents shall be archived safely and securely in such a way that ensures that they are readily available if required, and in compliance with the University of Pittsburgh guidelines. According to the University of Pittsburgh IRB, all study-related documents will be stored for 7 years. The investigator site file is not to be destroyed without approval by NIAMS or the Safety Monitor.

9.3 Publication Policy

Following completion of the TAMER study, the investigators will publish the results of this research in scientific journals. The International Committee of Medical Journal Editors (ICMJE) member journals has adopted a trials-registration policy as a condition for publication. This policy requires that all clinical trials be registered in a public trials registry such as ClinicalTrials.gov, which is sponsored by the National Library of Medicine. The TAMER study will be registered prior to commencement.

As this is a single-center study, there will be no publications committee. Authorship determination will be made in consultation with the co-investigators of the study (Drs. [name], [name] and [name]).

Publication of the results of this trial will be governed by NIAMS publication policies. Any presentation, abstract, or manuscript will be made available for review by the NIAMS supporters prior to its submission. [name] will maintain control of all TAMER-generated specimens and will decide on the scientific merit of any future sub-studies. They will adhere to the letter and the spirit of the prevailing NIH and NIAMS guidelines on the sharing of research resources produced from federally-funded research.

9.4 Confidentiality

This is a single-center study, with a relatively small number of subjects. All personnel involved in this study have undergone training and certification on the protection of human subjects, confidentiality, HIPAA compliance and research integrity. This training is conducted regularly by the University of Pittsburgh via an internet-based system of education in research.

The only individuals with access to identifiable information and treatment assignment will be the data manager and study statistician. Access to study data will be password protected. All linkage materials are stored separately and maintained in a secure area.

All blood samples will be collected in a de-identified manner using labels generated through the Rheumatic Disease Management System (RDMS) system, which is a Division-wide system for rheumatologic research. Linkage codes will be maintained by the data manager in the event of emergencies or future need, and these will be kept in a locked filing cabinet located in the Scleroderma Center research office.

10. Ethical and legal aspects

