6.2 Identity of study treatment

Atorvastatin

Atorvastatin will be supplied at 40 mg as film-coated, immediate-release tablets. All study drug and placebo tablets will be provided through the UPMC Investigational Drug Service, who will also be handling patient randomization.

A complete record of batch numbers and expiry dates of all study treatment, as well as the labels, will be maintained in the study file.

Matching placebo

Matching placebo tablets will appear identical to active atorvastatin tablets but will not contain active study drug.

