6.3 Treatment assignment

This is a randomized, double-blind, placebo-controlled, parallel-group, single-center study. Subjects who complete all screening procedures and meet all the eligibility criteria are to be randomized in a 1:1 ratio by the UPMC IDS.

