6.5 Blinding

The study will be conducted in double-blind fashion. Active atorvastatin and placebo tablet formulations will be identical in appearance (size, shape, color) and smell. The packaging and labeling will be designed to maintain blinded conditions for the investigator and the study team. The study data will remain blinded until database lock.

Emergency unblinding by the investigator

In case of emergency, the investigator is permitted to unblind individual cases. However, this will be restricted to cases of emergency where the unblinding result is of importance for the acute treatment strategy. The occurrence of an SAE should not routinely precipitate the immediate unblinding of the label. Date, time, and reason for unblinding will be captured. Unblinding will be coordinated through the Investigational Drug Service

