7.1.2.5 Premature discontinuation of study drug treatment

In the event of premature discontinuation of study drug treatment, subjects must undergo the same procedures as outlined for the Week 16 end of study visit if they have completed 8 weeks or more of therapy. If subjects discontinue prior to 8 weeks of therapy, then they will undergo the same procedures as outlined for Week 8. All subjects who discontinue study drug treatment early will have an additional 30 day safety follow-up visit.

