8.2.3 Safety

Tables of adverse events and serious adverse events will be created. These will be maintained by the data manager or study statistician and reported twice yearly to the Safety Officer. The internal Safety Officer will be appointed by the Principal Investigator. These tables will include masked treatment group. This is detailed in the Safety Monitoring Plan.

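### Section 9.4 gives the data manager and study statistician access to treatment assignment with no time limit, which contradicts blinding until database lock in 6.5

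*Combined protocol and SAP*

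**What the plan says.** Section 9.4 (Confidentiality) states: "The only individuals with access to identifiable information and treatment assignment will be the data manager and study statistician". The sentence has no time point, no condition and no restriction to masked codes.

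Section 6.5 (Blinding) states: "The study data will remain blinded until database lock". It also says that packaging and labels are meant to keep the investigator and study personnel blind. The one exception is for emergencies, where the investigator may learn an individual assignment: "Unblinding will be coordinated through the Investigational Drug Service".

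The allocation itself sits with IDS. Section 6.2 says of IDS, "who will also be handling patient randomization", and section 6.3 says that eligible subjects "are to be randomized in a 1:1 ratio by the UPMC IDS". Section 4.1.2 likewise has IDS run the randomisation centrally.

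Section 8.2.3 (Safety) has the data manager or study statistician maintain the adverse event tables and report them twice a year to the Safety Officer. On the grouping it says: "These tables will include masked treatment group". It then refers elsewhere: "This is detailed in the Safety Monitoring Plan". That plan is not among the documents supplied.

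**The concern.** A trial presented as double-blind should let a reader work out who could know the arm, and when. Here the answer depends on which section is read. Under 9.4 taken literally, the two roles closest to the data know each participant's treatment from randomisation onwards. Under 6.5 they do not.

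This matters because 8.2.2 leaves several choices to be settled on the data: whether to adjust for baseline differences, whether to transform, and whether to switch to a nonparametric method. Section 8.1 says that the aim is an effect-size estimate for a later phase 3 trial. Choices of this kind carry more weight if whoever makes them knows the arm and can see which option favours atorvastatin. If the protocol says that the statistician had the assignment throughout, a later reader has no way to rule that out, even if practice was sound.

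**Working it through.** The point is textual, so the check is a comparison of the passages. The one design figure in the plan, the half-width of 0.374 in 8.4, does not enter into it.

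| Section | Role | Position on treatment assignment | Period |
|---|---|---|---|
| 9.4 | Data manager, study statistician | Have access | Not stated |
| 6.5 | No role exempted | Study data blinded | Until database lock |
| 6.5, emergencies | Investigator, through IDS | Individual cases only | When acute treatment depends on it |
| 4.1.2, 6.2, 6.3 | IDS | Runs the randomisation | From enrolment |
| 8.2.3 | Data manager or study statistician | Tables by masked group | Twice-yearly reports |

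Three readings of 9.4 are possible.

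1. *Access applies throughout the trial.* This contradicts 6.5 directly. It also leaves little purpose in masking the 8.2.3 tables from the people who compile them.
2. *Access applies only after lock.* This agrees with 6.5 and 8.2.3, but 9.4 does not say it. The same sentence also governs identifiable information, which has to be handled while the trial is running. The sentence would therefore have to carry two different time limits, and it states neither.
3. *Assignment means a masked group label.* This agrees with 8.2.3, but again the text does not say it.

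A further sign that 9.4 needs rewording is its claim to be exhaustive. IDS must hold the code to randomise and to unblind in an emergency, and 6.5 lets the investigator learn an individual assignment in that event. Neither appears in the 9.4 list.

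Next, is there a stated need for the true assignment before lock? Section 8.3 plans no interim analysis. The safety tables use masked groups. Emergency unblinding goes through IDS. Section 3 lists the data manager and study statisticians among the study personnel and names no separate unblinded statistician. Nothing supplied describes a task for which either role needs the actual arm before lock.

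The linkage codes mentioned later in 9.4 are left out of this comparison. They appear in the paragraph on blood samples and seem to link samples to identity, not to treatment.

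**The case against.** The best defence is that 9.4 is a confidentiality clause whose purpose is to restrict access, not to set the blinding rules. The two more specific sections, 6.5 and 8.2.3, both point towards masking, and read together with them 9.4 can be taken as loose wording for the period after lock. The Safety Monitoring Plan may settle the matter. No passage assigns data cleaning or pre-lock analysis decisions to these roles. The primary outcome in 7.5.4 is a ratio computed from device readings by a set formula, so the exposure is confined to data handling and analysis choices. Much of this stands, and it limits how far the point can go. It does not remove the contradiction, because the limiting words are absent from 9.4.

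A reader might infer that the data manager and statistician will in fact be unblinded during the trial. The documents do not support that: they contain two incompatible statements and no description of what is actually done.

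A reader might also try to attach a bias to the conflict through the early-termination visits. Under 7.1.2.5, participants who stop study drug early "must undergo the same procedures as outlined for the Week 16 end of study visit if they have completed 8 weeks or more", and the plan does not say whether that EndoPAT reading counts as the week 16 value. Any figure would need an assumed stopping rate, which the documents do not give, and an assumption that the choice is deliberately made to favour atorvastatin. It would mainly measure the missing rule for early readings, which is a separate point and would remain whoever held the code.

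**Conclusion.** The contradiction is real, and nothing in the supplied text resolves it: 9.4 gives two roles access to treatment assignment without a time limit, while 6.5 keeps study data blinded until lock without exempting them. It is an inconsistency about who is blinded, not a demonstration of unblinding or of bias. No numerical size is given because the documents do not support one.

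The conclusion rests on the protocol and SAP alone. A clear statement in the Safety Monitoring Plan could show that practice is already sound, but 9.4 would still need to agree with 6.5. The point is worth acting on because the double-blind claim depends on it and the correction is small.

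**What to change.** Amend 9.4 to say that, until database lock, IDS holds the randomisation code and the data manager and study statistician work only from masked group codes, with access to actual assignment after lock. This agrees with 6.2, 6.3, 6.5 and 8.2.3.

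Custody by IDS is not the only acceptable solution. If the Safety Monitoring Plan gives someone a task that needs the code earlier, name that person as an exception in 6.5 and keep them out of data cleaning and analysis decisions. Section 3 lists more than one study statistician while 9.4 refers to one, so such a separation may be feasible.

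The cost is a sentence in 9.4, or a named exception in 6.5, plus the work for IDS of supplying masked group codes for the safety tables. No visits or participants are added. The handling of early EndoPAT readings and the rule for transformations in 8.2.2 should be raised as separate points; this amendment does not settle either.

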10.1 Ethical and legal conduct of the study

The procedures set out in this protocol, pertaining to the conduct, evaluation, and documentation of this study, are designed to abide by GCP guidelines and under the guiding principles detailed in the Declaration of Helsinki. IRB approval has been obtained. The investigator may implement a deviation from, or a change of, the protocol to eliminate an immediate hazard(s) to the trial subjects without prior IRB approval. As soon as possible, the implemented deviation or change, the reasons for it and if appropriate the proposed protocol amendment will then be submitted to the University of Pittsburgh IRB. Any deviations from the protocol will be explained and documented by the investigator. Protocol deviations will also be reported biannually to the Safety Monitor.

